A8. Therapeutic Intent

Does this trial have therapeutic intent?

Yes

A9. ClinicalTrials.gov Registration

Does this protocol/trial require registration on ClinicalTrials.gov due to it: meeting the definition of an Applicable Clinical Trial, being required under the terms and conditions of an award, or being proposed to be published in ICMJE journals?

Yes

Who will be responsible for registering and maintaining the registration of this Applicable Clinical Trial?

The BCM PI will register the trial because either:

- the trial is BCM PI-initiated,
- BCM is the lead site of this multicenter trial, or,
- the industry sponsor has instructed the BCM PI to register the trial, or,
- registration of this trail is required as a term and condition of the reward by the funding agency.

ClinicalTrials.gov Identifier:

NCT

Section B: Exempt Request

B. Exempt From IRB Review

Not Applicable

Section C: Background Information

Critically ill patients often suffer from hospital acquired weakness. This condition may originate from Neurogenic (critical illness Polyneuropathy or CIP) or Myogenic (critical illness Myopathy or CIM) disturbances, or a combination of both (critical illness Neuro-Myopathy or CINM). Moreover, prolonged hospital stay has been associated with pronounced loss of muscle mass that can exceed 10% over the 1st week, which leads to functional impairment and complications post-hospital discharge. Prevalence of hospital-acquired weakness varies widely depending on patient population and risk factors, assessment period, diagnosis method, and patients pre-hospital functional status (age-related frailty).

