Phase II: 20 additional subjects with post-COVID-19 infection coming to the COVID-19 clinic at Baylor College of Medicine for treatment of complications (i.e., hospital acquired weakness due to neuromyopathy). Patients will begin the study after being diagnosed with neuromyopathy due to prolonged hospitalization for COVID-19. This will be performed by a critical care and pulmonary specialist at the BCM COVID-19 Clinic. The entire cohort will receive daily electrical stimulation in lower extremity (e.g. Gastrocnemius, tibial anterior muscle) up to 1 hour to recover from Neuromyopathy complications and prolonged hospital stay. The patients will take the device home up to 4 weeks and will be screened once a week at the COVID-19 clinic for neuromuscular evaluation.

Inclusion Criteria:

Age: Adults age 18 years or older Disease status: COVID-19 test positive Critically ill requiring care in the hospital.

Patients must have been previously hospitalized due to COVID-19 infection and diagnosed with hospital acquired weakness by pulmonary care specialists. Patients will have to be alert and conscious to sign the consent form.

Exclusion Criteria:

Subject has a demand-type cardiac pacemaker, implanted defibrillator or other implanted electronic device Active wound infection Below the knee amputations Based on the clinicians decision whether the patient is eligible for the study.

F2. Procedure

Phase I:

Aim1 (to understand mechanism of action): Examine immediate benefit of lower extremity EE to improve venous return flow, tissue oxygenation, and muscle activation (short term benefit). In this study, we will recruit a convenient sample of 20 hospital patients diagnosed with COVID-19 (short-term benefit).

Optional: Subjects will be assessed using Doppler ultrasound and near infrared imaging (Kent Imaging System) at pre-, 30min, 60min, and 30min post-treatment (after stopping of EE device). Lower extremity muscle activation will be assessed by using sEMG (electromyography).

Patients will begin the study after being admitted to the hospital no more than 48 hours.

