The protocol will consist of 4 weeks of lower-extremity electrical stimulation. Opposite to our initial study, this modality will consist of home-based therapy, meaning that the patient will take the device home and attend the clinic once a week for screening and assessment of therapy.

The protocol will be performed as the following description: This trial will have 20 patients divided in two groups. Group 1 (intervention, n=10): Will receive an active Tennant Biomodulator Group 2 (control, n=10): Will receive an inactive Tennant Biomodulator This study will consist of 5 visits total and one phone interview 12 weeks after baseline for both groups. The patient will be compensated \$50 per visit (total \$250), with free parking. Payment will only be available for subjects who participate in Part II.

During the first and last visit, the research staff will turn the Tennant Biomodulator PRO® on for one hour and measure any changes in muscle strength, endurance, and blood flow after the therapy. Once the first visit is over, the patient will take the Tennat Biomodulator® home and will be instructed to turn it on for one hour every day for four weeks.

The visits in-between will be performed in the following order: 1) Questionnaires (pain, weakness, sleep, quality of life, frailty, depression, life and space, beck anxiety scale, Katz-daily living) 2) Musculoskeletal assessments (non-invasive surface electromyography, vibration perception threshold) 3) Vascular assessments (non-invasive Near infra-red spectroscopy)

After 4 weeks, the patients will turn back the device to the research staff.

The supervision of this study will be by pulmonary care specialists, and the location will be at the recently open COVID-19 clinic at Baylor College of Medicine.

Section G: Sample Size/Data Analysis

G1. Sample Size

How many subjects (or specimens, or charts) will be used in this study?

Local: 40 Worldwide: 40

Please indicate why you chose the sample size proposed:

Sample size is convenient and selected based on available resources to demonstrate feasibility and the proof of concept effectiveness of EE therapy for COVID-19 patients admitted to ICU and post-ICU. We plan to recruit 40 eligible subjects.

G2. Data Analysis

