Provide a description of your plan for data analysis. State the types of comparisons you plan (e.g. comparison of means, comparison of proportions, regressions, analysis of variance). Which is the PRIMARY comparison/analysis? How will the analyses proposed relate to the primary purposes of your study?

P-values of 0.05 or less will be considered statistically significant based on a two-sided test unless otherwise noted. All variables will be tabulated descriptively at each scheduled time point (baseline and discharge date). For each continuous variable, the analyses will include the mean, standard deviation, minimum and maximum. For each categorical variable, the summary will include frequencies and percentages. Each variable will be analyzed using all available data. Baseline variables will be summarized using descriptive statistics. We assume that a successful intervention is also helpful to maintain subjects muscle mass, reduce neuromyopathy signs and increase venous return flow. The measured parameters (e.g. muscle circumference, sEMG, kent imaging, doppler, etc.) should change substantially from baseline to the end of the intervention. For example, the EMG amplitude values should show increased voltages. Next, for all continuous variables, pre-treatment scores will be regressed on post-treatment scores to form residualized change scores (e.g. sEMG, VPT, dynamometer, etc). Correlations will then be generated among these scores to determine whether changes in sEMG factors are related appropriately with increases in (clinically assessed) functional capacities and self-report measures of activities. ANOVA test will be used to examine significant difference between patients with severe risk factors for prolonged ICU stage (e.g. age, BMI, cardiovascular morbidities). Moderator effects will also be examined for exploratory purposes. Using gender as an example, mixed design ANOVAs will be conducted to determine whether mobility factors change over

the course of treatment at different rates or with different patterns for men and women. Additional analyses will test whether changes in muscle strength and neuropathy (e.g. VPT and dynamometer assessment at time of discharge).

Section H: Potential Risks/Discomforts

H1. Potential Risks/Discomforts

Describe and assess any potential risks/discomforts; (physical, psychological, social, legal, or other) and assess the likelihood and seriousness of such risks:

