Describe potential benefit(s) to be gained by the individual subject as a result of participating in the planned work.

There is potential benefit of prevention or improvement of hospital acquired weakness due to prolonged hospital stay for participants, based on previous studies the electrical stimulation will improve blood flow, tissue perfusion and muscle activation. The device is used to reduce pain. However, the proposed treatment may assist in preventing or improving hospital-acquired Weakness because of prolonged hospital stay . In addition, the participation in this study may help the investigators better understand how COVID19 may impact cause myopathy and neuropathy and how to best help these patients to recover from prolonged hospital-stay .

Primary outcomes include neuropathy (assessed using VPT test); muscle function (assessed using sEMG), and tissue oxygenation (assessed using Kent Imaging). Secondary outcomes include weakness (assessed using dynamometer); muscle atrophy (assessed by weight loss as well as measuring ankle, calf, and thigh circumference); venous return flow (Doppler US [optional]); frailty (frailtymeter [optional]); hospital length of stay (patient medical record); and major adverse events (patient health record). The primary and secondary outcomes will be assessed at baseline (if feasible) and on biweekly basis up to 4 weeks or hospital discharge, whichever came first. Appropriate mixed models (linear for continuous or Generalized Estimating Equations (GEEs) for non-continuous or non-parametric variables) will be used to test the intervention effect for each of the primary (e.g., tissue perfusion, tissue oxygen delivery, neuropathy severity, and

myopathy incident) or secondary (e.g., frailty, weight loss, MAE, etc) outcomes.

Also, participation may help the investigators design a practical assessing method to identify the impact of neuromyopathy in the hospital setting. This may allow physicians to provide personalized care by monitoring muscle loss and limb complications caused by prolonged hospital length of stay.

Describe potential benefit(s) to society of the planned work.

As described above, this type of work may allow physicians to provide more personalized care for hospitalized patients in need of physical therapy for continuous and prolonged periods, specially when having a severe illness that includes medical staff risk contact.

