Title: Electrical Stimulation Therapy for Preventing Hospital-acquired Weakness in Critically Ill COVID-19 Patients - A Proof of Concept Randomized Controlled Trial

Identifier: NCT04685213

Date: May 21, 2021

Statistical analysis plan

Shapiro-Wilk test ($p > 0.05$) was used to assess the normality of data. Independent t-test was used for group comparison at baseline on normally distributed continuous demographics, clinical data, and sEMG parameters. Mann-Whitney U test was used if the assumption of normal distribution was not satisfied. For categorical variables, Chi-square test was used to compare between-group differences at baseline. The effect size for baseline continuous and categorical data were measured using Cramer's V and Cohen's d, respectively. Generalized estimating equations (GEE) was used to test the main effect of group (two levels: CG and IG), time (three levels: baseline, 3 days, and 9 days), and their interaction on the outcome measures regardless of data unable to obtain due to the patients' critical condition. Pearson correlation was used to associate baseline values with %change of outcomes at 9 days. For those significant associations, multiple linear regression was used to determine the relationship between those significantly associated variables. The model performance was reported in terms of variance (R^2), and p-value. For all tests, an alpha level of < 0.05 was considered statistically significant.

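### The SAP correlates undefined baseline values with percentage change at day 9; for an outcome paired with its own baseline, a significant r is not by itself evidence that response depends on baseline

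*SAP*

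**What the plan says.** The SAP sets out the main analysis as GEE tests of group, time (baseline, 3 days, 9 days) and their interaction. It then adds a second step: "Pearson correlation was used to associate baseline values with %change of outcomes at 9 days". The next sentence reads: "For those significant associations, multiple linear regression was used to determine the relationship between those significantly associated variables". That regression is reported by R² and p, and one alpha of 0.05 applies to all tests.

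The SAP does not list the baseline values. The nearest guide is its sentence on baseline group comparisons, which covers "normally distributed continuous demographics, clinical data, and sEMG parameters". In the Protocol (Section I), the primary outcomes include "muscle function (assessed using sEMG), and tissue oxygenation (assessed using Kent Imaging". So sEMG is both a baseline variable and an outcome. Nothing in the SAP excludes pairing an outcome with its own baseline, and nothing says that the correlation or the regression adjusts for group or for the outcome's baseline.

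**The concern.** Percentage change is 100 × (day 9 − baseline) / baseline. If the same baseline is also the predictor, it enters both sides of the correlation. The test of r = 0 then generally does not test whether response is independent of baseline, because r can differ from zero through the formula and through regression to the mean. A predictor correlated with that baseline can inherit part of the same association.

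At stake is interpretation. A reader could take a significant r, and the R² of a regression built from pairs that passed this test, as showing which patients change more. It may only reflect how percentage change is constructed.

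**Working it through.** **Figure to reproduce.** None. The documents give no r, SD, reliability, power or analysed n for this step.

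**Inputs.**
- n: at most 20. The Protocol (F2, Phase I) says "we will recruit a convenient sample of 20 hospital patients diagnosed with COVID-19". Phase II has no day-9 visit, since "the patient will take the device home and attend the clinic once a week for screening and assessment of therapy". That the SAP analysis uses only hospital patients is an inference. Values of 10 and 14 allow for missing day-9 data.
- Alpha 0.05 (SAP), two-sided (Protocol G2). Critical |r| is 0.632, 0.532 and 0.444 at n = 10, 14 and 20.
- Assumed, not in the documents: lognormal outcome, equal distributions at both visits, CV 0.2–0.4, baseline to day-9 correlation ρ of 0.5, 0.7 or 0.9.

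**Algebra on the log scale.** Let X be the baseline, Y the day-9 value, each with log-variance s².
- Cov(log X, log Y − log X) = −(1 − ρ)s²
- Var(log Y − log X) = 2(1 − ρ)s²
- Hence r = −√((1 − ρ)/2), which is −0.50, −0.39 and −0.22 for ρ = 0.5, 0.7 and 0.9.

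**Approximate rejection at n = 20** (Fisher z, standard error 1/√17, √17 = 4.123):
- ρ = 0.5: 0.549 × 4.123 = 2.26; 2.26 − 1.96 = 0.30; about 62%
- ρ = 0.7: 0.409 × 4.123 = 1.68; 1.68 − 1.96 = −0.28; about 39%
- ρ = 0.9: 0.227 × 4.123 = 0.94; 0.94 − 1.96 = −1.02; about 15%

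**Simulation with percentage change itself** (20,000 datasets per setting; own-baseline pair):

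| ρ | mean r | n = 10 | n = 14 | n = 20 |
|---|---|---|---|---|
| 0.5 | about −0.46 | 25–32% | 38–46% | 56–64% |
| 0.7 | about −0.36 | 15–19% | 23–27% | 34–39% |
| 0.9 | about −0.21 | 8–9% | 10–12% | 14–16% |

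The ranges cover the CVs, simulation error, and whether ρ is set on the raw or log scale, so differences of a point or two carry no meaning. A common proportional shift at day 9 only rescales percentage change linearly and leaves r identical.

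**Other predictors.** A predictor correlated 0.5 with the outcome's baseline, with no direct link to day 9, is rejected in about 10% / 13% / 18% of datasets (n = 10 / 14 / 20) at ρ = 0.5 and about 6% / 7% / 7–8% at ρ = 0.9. An unrelated predictor is rejected in about 5%.

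**Dependence on the model (own-baseline pair).**
- Proportional change independent of an error-free baseline, or additive change with zero mean independent of baseline: 4.6–5.4%.
- The proportional case with measurement error (reliability 0.9 to 0.7): 7–28% at n = 20, r from −0.10 to −0.32.
- Additive change with a mean shift of 10% of the median baseline and SD 10–20% of it (assumed): r from +0.09 to +0.30 for a fall and −0.09 to −0.30 for a rise; about 7–26% at n = 20 for either direction.

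**The alternative.** Regressing the day-9 value on the predictor (correlated 0.5 with baseline, no direct link), the outcome's own baseline and group gives 4.7–5.3% rejection under the lognormal model, where the unadjusted correlation gives up to 18%.

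**The case against.** The strongest reply is that the fault is conditional. The SAP never says that an outcome is paired with its own baseline, and its baseline variables also include demographics and clinical data. It says only that values are associated, and it does not claim to identify responders. The step is ancillary in a proof-of-concept trial. All of this stands and limits the point, but it does not remove it: the text permits own-baseline pairs and, unlike the Protocol's moderator analyses (G2), does not label the step exploratory.

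The rates come from one assumed model, and other plausible models give about 5% or a different sign. That also stands. The figures illustrate what can happen and do not estimate what did.

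The remedy is not better in every case. If the baseline is noisy and the predictor tracks the true level (correlation 0.5), the adjusted test rejects 6–7% / 7–9% / 7–12% at n = 10 / 14 / 20 (reliability 0.9 to 0.7), while the percentage-change correlation stays near 5%.

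Two further inferences are tempting but unsupported:
- The muscle loss cited in Protocol Section C might seem to predict the direction of the artefact. It concerns muscle mass, not sEMG, and G2 expects EMG amplitude to rise.
- Percentage change might seem to contradict the residualized change scores in G2. Those scores are for correlating changes with other changes, which is a different analysis, so the two need not be reconciled here.

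**Conclusion.** The point holds in conditional form. The SAP leaves its baseline values undefined and admits own-baseline pairs. For such a pair a significant r, or an R² built on it, is not by itself evidence that response depends on baseline. Predictors correlated with that baseline are affected less, and unrelated ones not at all.

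Under the stated lognormal assumptions the excess over 5% ranges from small (14–16% at ρ = 0.9, n = 20) to large (56–64% at ρ = 0.5, n = 20). Neither size nor sign can be fixed from the documents.

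A reader might infer that own-baseline correlations were run, that every significant correlation here is spurious, or that the treatment comparison is compromised. The documents support none of these. The pairs are not listed, some models give no excess, and the GEE tests of group, time and interaction do not use this step. The change should be made, but it does not bear on the main analysis.

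**What to change.** 1. List the variables meant by baseline values.
2. Do not test an outcome's own baseline against its percentage change.
3. For the other predictors, name a few in advance instead of selecting on p < 0.05. Regress the day-9 value (log scale if skewed and positive) on the predictor, the outcome's own baseline and group.
4. Label the step exploratory and describe results as association given the measured baseline, not as response.

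**Cost.** No new data. The SAP is written in the past tense, so some reanalysis as well as new wording is needed. Fewer associations will be significant: power at n = 10 / 14 / 20 is 25% / 39% / 59% for a partial correlation of 0.5 and 55% / 78% / 94% for 0.7. The mild inflation possible with a noisy baseline is the reason for the wording in item 4.

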For patients who lack the capacity to consent, the investigator/designee may explain the study to the legally authorized representative by phone. The discussion will be documented in the subject's medical record or research chart. Two copies of the unsigned consent form will be sent to the subject/legal representative with instructions for completion of the signature page and assent (if applicable). Signatures will be obtained according to standard Baylor IRB regulations. The subject will be told to keep one form and returned the other to the investigator by mail, email, or fax. The Baylor Investigator/designee will sign the consent form when returned from the subject. The signed consent form will be maintained in research records.

E3. Pregnant woman/fetus

Will pregnant women and/or fetuses (as described in 45 CFR 46 Subpart B) be enrolled in the research?

No

E4. Neonates

Will neonates of uncertain viability or nonviable neonates (as described in 45 CFR 46 Subpart B) be enrolled in the research?

No

E5. Children

Will children be enrolled in the research?

No

Section F: Design/Procedure

F1. Design

Select one category that most adequately describes your research:

c) Pilot

Discuss the research design including but not limited to such issues as: probability of group assignment, potential for subject to be randomized to placebo group, use of control subjects, etc.

Phase I: 20 subjects with COVID-19 infection that are being treated in the hospital. This means that this patient population is positive to COVID-19, are hospitalized, or develop severe symptomatology, but they have been admitted with no more than 48 hours to the hospital. Also, in some cases the patients will not be able to consent at the time of enrollment determines a high grade of severity of illness. The entire cohort will receive daily electrical stimulation in lower extremity (e.g. Gastrocnemius, tibial anterior muscle) up to 1 hour to decrease Neuromyopathy complications and prolonged hospital stay. Due to the condition of the patient we are looking to reduce the interaction with staff, the device will be placed with no additional requirements. Physical therapy targets other physical performances, this device is aimed to improve blood flow, tissue perfusion and muscle activation while the patient is non-responsive to physical activities.

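### The SAP selects baseline predictors by p<0.05 and refits them on the same patients, so the R² and p-value it reports as model performance are uncorrected for selection

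*SAP*

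**What the plan says.** The single paragraph of the SAP sets out a two-step rule. The screen comes first: "Pearson correlation was used to associate baseline values with %change of outcomes at 9 days". The refit follows: "For those significant associations, multiple linear regression was used to determine the relationship between those significantly associated variables". The output is then defined: "The model performance was reported in terms of variance (R^2), and p-value". The threshold is common to everything: "For all tests, an alpha level of < 0.05 was considered statistically significant".

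The SAP does not list or count the baseline variables or the outcomes. For this analysis it mentions no multiplicity control, no adjusted or validated R², and no exploratory label. It does not say whether the correlations are pooled or done by group, or whether group enters the regression.

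The SAP states no sample size. The protocol gives 20 for the inpatient phase (F1: "Phase I: 20 subjects with COVID-19 infection that are being treated in the hospital") and 20 for the home-based phase (F2: "This trial will have 20 patients divided in two groups"). Two-sided testing is stated only in protocol G2: "P-values of 0.05 or less will be considered statistically significant based on a two-sided test unless otherwise noted".

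**The concern.** A variable reaches the regression because it has already shown a large correlation with the outcome in these patients. Fitting it again to the same patients and quoting R² and p uses the same evidence twice. With a small sample the selection threshold is itself a large correlation, so the reported fit starts high whether or not anything real is present.

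At stake is the credibility of any statement that a baseline characteristic predicts response to stimulation. The problem applies to any candidate variable. It is separate from the mathematical coupling that arises when a variable's baseline is correlated with its own percentage change.

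**Working it through.** The plan has no figure of its own to reproduce on this point.

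**Inputs.** Alpha 0.05 for every test (SAP); two-sided (protocol G2); n=20 (protocol F1 and F2, since the SAP gives none). The SAP expects some data to be unobtainable, so n=16 and n=12 are shown as assumed lower values. Assumed because the documents do not give them: 5, 10 or 15 candidates per outcome, and correlation among candidates of 0, 0.5 or 0.7.

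**1. Minimum R².** A Pearson correlation is significant when r² ≥ t²/(t² + n − 2), with t the two-sided 5% critical value on n − 2 degrees of freedom.

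- n=20: t=2.101, so r² = 4.414/(4.414 + 18) = 0.197 and |r| = 0.444.
- n=16: t=2.145, so r² = 4.601/(4.601 + 14) = 0.247.
- n=12: t=2.228, so r² = 4.964/(4.964 + 10) = 0.332.

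Adding terms, including group, cannot lower R² in the same patients. The minimum therefore holds for any number of candidates, provided the refit uses the patients who were screened.

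**2. p-value with one selected variable.** A regression on that variable alone gives the same test as the correlation, so its p-value is below 0.05 automatically.

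**3. Chance of a model when nothing is related, independent candidates.** 1 − 0.95^k gives 0.226 (k=5), 0.401 (k=10) and 0.537 (k=15) per outcome, against a nominal 0.05.

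**4. Simulation of the whole procedure with no true relationship, n=20.** Ranges within a cell are differences between separate simulation runs.

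| Candidates | Correlation among them | Model reported | Refit p<0.05, given a model |
|---|---|---|---|
| 5 / 10 / 15 | 0 | 22–23% / 40–41% / 52–54% | 99% or more |
| 5 / 10 / 15 | 0.5 | 18–19% / 30% / 37–38% | 92–94% / 85–86% / 81% |
| 5 / 10 / 15 | 0.7 | 15% / 22% / 27% | 78% / 67% / 58% |

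Mean R² of the reported models is 0.29 / 0.31 / 0.33 with independent candidates, and about 0.29–0.32 with correlated ones. In runs with 5 to 20 candidates and correlation 0 or 0.5, the median reported R² was 0.26–0.32, while the median R² of the same models in new patients was −0.33 to −0.39. At n=16 with 10 independent candidates, a model is reported for 40% of outcomes with mean R² 0.37.

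**5. When one predictor is real.** With one true predictor (r=0.6, so true R² = 0.6² = 0.36) among 5 independent candidates at n=20, the true predictor is in 96% of models and mean reported R² is 0.44. The excess is 0.44 − 0.36 = 0.08.

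**6. What repairs it.** With no screen, a prespecified model with 2 or 3 predictors at n=20 has a null false-positive rate of 0.050 or 0.051 and median R² of 0.08 or 0.13. A Bonferroni screen (0.05/k, k = 5, 10, 20) brings the chance of a model from noise to about 0.05, but the median R² of models that pass is still 0.36–0.45. Tightening the screen alone does not correct R².

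**The case against.** The best defence is that this is a secondary analysis in a pilot. Protocol G1 says so of the design: "Sample size is convenient and selected based on available resources to demonstrate feasibility". No decision rule uses the regression, and the comparison of groups rests on the GEE. That limits the damage, but it does not make the reported R² and p-value correct, and a small sample makes the bias larger. Protocol G2 calls its moderator analyses exploratory, but those are mixed-design ANOVAs; the SAP attaches no such label to this regression.

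Four stronger readings are tempting and go too far.

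- *The p-value cannot fail.* This is true only when one variable is selected. The figure of 99% needs independent candidates, and demographic, clinical and sEMG measures on the same patients are plausibly correlated. The share then falls to about 58–92%.
- *The R² is nothing but noise.* That holds only if no candidate is related to the outcome. Step 5 shows a case where most of the reported R² is real.
- *The predictors will be used to select patients for a later trial.* The documents do not say this. Protocol F2 earmarks length of stay and major adverse events for planning future studies, not baseline correlates.
- *The analysis is known to use 20 patients.* That number is inferred from the protocol. The number with day-9 data may be lower, which would raise the minimum R².

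**Conclusion.** The concern stands for the baseline-predictor analysis only. The minimum R² of 0.197 follows from alpha 0.05 two-sided and n=20, whatever the number of candidates. The chance of reporting a model from noise, about 22–54% of outcomes with independent candidates and 15–37% with correlated ones, rests on the assumed 5 to 15 candidates and on there being no true relationship. The honest description of the reported figures is an R² that is too high by an unknown amount and a p-value that does not carry its nominal meaning. A reader might infer that the trial's test of the intervention is compromised; it is not, because the group-by-time GEE does not use this selection. The change should be made, but it does not bear on the main comparison.

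**What to change.** If the two-step rule is kept:

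- list and count the candidate baseline variables and the outcomes;
- replace the naive R² and p-value by an R² from cross-validation or bootstrap that repeats the screening in every resample;
- give a permutation p-value for the whole procedure, screening included;
- label the result exploratory.

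This needs only the existing data, so it remains possible if the analysis has already been run, as the SAP's past tense may suggest.

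If it has not been run, an alternative is one model per outcome fixed in advance: day-9 value on group, its own baseline, and a predictor chosen on clinical grounds with the reason stated, reported with a confidence interval. This removes the selection within each outcome, but multiplicity across outcomes remains and the number of outcomes should still be stated.

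The cost is a change of SAP wording, a little more code, and probably fewer predictors declared significant.
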